4.5.2 Exposure Days

An Exposure Day (ED) is defined as any day that the subject inhaled at least one full or partial dose of IMP as defined in Section Error! Reference source not found., either at the investigational site or at home regardless of the number of doses on that day. The number of EDs per subject will be summarised overall and by treatment group for the Safety and mITT Populations using descriptive statistics for continuous variables.

4.5.3 Extent of Exposure

Extent of exposure (days) will be calculated using the following formula:

- Extent of exposure (days) = Date of last full or partial inhaled dose of IMP - date of first full or partial inhaled dose of IMP + 1.

The date of last full or partial inhaled dose of IMP is as defined in Section Error! Reference source not found..

The extent of exposure will also be calculated in weeks using the following formula:

- Extent of exposure (weeks) = Extent of exposure (days) / 7.

Dose of IMP either at the investigational site or at home will be considered.

Treatment exposure will be summarised overall and by treatment group for the Safety and mITT Populations using descriptive statistics for continuous variables.

4.5.4 Adherence

Adherence will be calculated overall.

The evaluation of adherence will be based on the following formula:

- Adherence (%) = (# Total Inhaled Doses / # Scheduled Doses)*100.

The total number of inhaled doses of IMP will be computed as described in Section 4.5.1. In cases where, due to the Covid-19 pandemic, the final dose registered on the CCI device is the dose given at the in-clinic part of a split Visit 7 for the purposes of bronchospasm testing, any dose on the CCI that is later than the date of last IMP administration as entered on the End of Study eCRF form will not be counted as an inhaled dose for the calculation of IMP adherence.

The scheduled doses will be computed as 2 times the total number of days from Visit 2 to the end of period date, i.e. (End of period date – date of Visit 2) + 1.

For the overall adherence, the end of period date will be the date of the last inhaled dose of IMP, based on the latest of the last dose recorded in the CCI download (with the exceptions

CONFIDENTIAL

Sponsor:	Zambon S.p.A.	Protocol Number:	Z7224L01
----------	---------------	------------------	----------

noted above relating to split Visit 7's) or the date of the last dose of IMP recorded in the End of Study form in the eCRF.

Adherence will be summarised by treatment group and overall for the mITT Population, presenting descriptive statistics for continuous variables and absolute and relative percentages of subjects considered to be adherent, i.e. with a least 80% of adherence.

An additional summary displaying the number and percentage of subjects in the following categories will also be presented by treatment group:

- <60%;
- 60 to <70%;
- 70 to <80%;
- 80 to <90%;
- ≥90%.

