Resolution of a NCFB pulmonary exacerbation is defined as the date of completion of the required course of systemic antibiotic treatment or the Investigator's judgement that the NCFB pulmonary exacerbation has resolved, whichever is later. Exacerbations occurring less than 14 days after the end of a course of systemic antibiotics for a NCFB pulmonary exacerbation will be considered as a single event (see [Section 9.1.5](#)).

IMP administration may be temporarily interrupted during the time of systemic antibiotic treatment due to a pulmonary exacerbation based on the Investigator's judgement; thereafter, the study treatment should restart as soon as possible. Stop date and re-start

date will be recorded in the relevant eCRF. The occurrence of a pulmonary exacerbation does not mandate the discontinuation of the subject from the trial, unless it occurs between Visit 1 and Visit 2 and /or the Investigator believes discontinuation is in the subject's best interest.

The following assessment will be performed at an Exacerbation Visit or Phone contact, and all details of the pulmonary exacerbation have to be recorded:

- start date and duration of all symptoms since the start;
- all symptoms present which support the NCFB pulmonary exacerbation diagnosis;
- all concomitant medications, especially systemic antibiotics;
- physical examinations and vital signs (if attending the clinic);
- date of CCI [REDACTED] and/or days of CCI [REDACTED] (if any);
- measurement and recording of FEV₁ and FVC (if feasible);
- pulmonary exacerbation as AE/SAE according to protocol and followed until resolution, including weekly follow-up phone calls as detailed above;
- collection of CCI [REDACTED] for other antibacterial panels. If subjects are unable to attend the clinic then suitable arrangements will be made to obtain an additional CCI [REDACTED], if feasible.

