3.5.4 Per-Protocol Population

The Per-Protocol Population (PP) will include all mITT subjects who were considered compliant with study drug administration (i.e. had an adherence of at least 80%) and who had no major protocol deviations that were considered as potentially impacting the efficacy results.

Major protocol deviations might include, but are not limited to, subjects taking a not-permitted concomitant medication, the IMP not being administered during the trial as defined in the protocol, subjects receiving a treatment different than the one assigned by randomisation. Categories of protocol deviations and additional details are reported in Section 4.10. The exact definition of major protocol deviations impacting the efficacy results will be discussed by the

CONFIDENTIAL

Sponsor:	Zambon S.p.A.	Protocol Number:	Z7224L01
----------	---------------	------------------	----------

study team during the blind review of the data and described in the Blind Data Review and Analysis Sets Report.

Results of the primary and relevant secondary efficacy endpoints analyses conducted for the PP will be considered as supportive.

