4.1.7 Definition of Follow-up Time

All the efficacy analyses are focused on the endpoints collected during the treatment period. For these analyses, the follow-up time will not include the time from end of treatment to the follow-up call.

The follow-up time in days will be calculated using the following formula:

- Follow-up time (days) = [date of treatment completion/discontinuation - date of first IMP dose + 1].

The follow-up time in years will be calculated using the following formula:

CONFIDENTIAL

Sponsor:	Zambon S.p.A.	Protocol Number:	Z7224L01
----------	---------------	------------------	----------

- Follow-up time (years) = Follow-up time (days) / 365.25.

Date of treatment completion will be the date of End of Treatment Visit.

Date of treatment discontinuation will be the date of End of Study Visit for subjects who discontinued the study before the End of Treatment Visit. In case a subject is lost to follow-up, the date of treatment discontinuation will be the date of last Study Visit.

Date of last Follow-up will not include any visits/calls after the end of treatment.

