The number of subjects considered in the model will be provided by treatment group. P-values of the effects based on the Wald chi-square test will be presented. Treatment effect (colistimethate sodium vs placebo) will be presented as the adjusted hazard ratio with the associated 95% Wald CIs. An adjusted hazard ratio <1 will indicate that colistimethate sodium increases the CCI compared to placebo.

To investigate the impact that discontinuations may have on the trial results, a CCI analysis will be conducted for the mITT Population. Discontinuers will be counted as failures with their last follow-up date, i.e. date of discontinuation, considered as the time of event.

The main analysis will also be repeated considering the subgroup of mITT subjects who were considered adherent, i.e. had an adherence until the first pulmonary exacerbation of at least 80%.

CCI Analysis for the Effect of Concomitant Antibiotic Therapy

A supportive analysis examining the impact of antibiotic use (by adding an additional covariate to the Cox proportional hazard regression model so that the hazard ratio is adjusted for this) will be conducted to determine if the use of antibiotics for conditions other than CCI has any impact on CCI.

The list of medications coded to WHO-DD Preferred Terms for antibiotics and anti-pseudomonal antibiotics are included in Appendix 3. If any medication in the list has a related CCI, the response to the question "CCI" on the CCI page for that CCI will then be checked to see whether or not the CCI in the opinion of the Investigator. If answered "No", the medication was not taken for a CCI and will be included as antibiotics used for conditions other than a CCI. Medications in the resulting list that do not have a related CCI will also be checked and included as antibiotics used for conditions other than a CCI.

Two additional tables will be presented:

- Supportive Cox proportional hazards analysis with use of any antibiotics for conditions other than a CCI (Yes/No) as an additional covariate.

CONFIDENTIAL

Sponsor:	Zambon S.p.A.	Protocol Number:	Z7224L01
----------	---------------	------------------	----------

- Supportive Cox proportional hazards analysis with use of any anti-pseudomonal antibiotics for conditions other than a protocol-defined pulmonary exacerbation (Yes/No) as an additional covariate.

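### The 80% adherence cut stops at the last inhaled dose and counts permitted exacerbation interruptions as missed doses, so it can admit early stoppers and can exclude subjects because of the primary outcome

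*SAP*

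**What the plan says.** SAP 4.5.4 gives the formula "Adherence (%) = (# Total Inhaled Doses / # Scheduled Doses)*100". For the denominator, "The scheduled doses will be computed as 2 times the total number of days from Visit 2 to the end of period date". The end of that period is then fixed: "For the overall adherence, the end of period date will be the date of the last inhaled dose of IMP", taken as the later of the device log and the End of Study form, with an exception for a Visit 7 split by Covid-19. Nothing is subtracted for interruptions.

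The rate analysis uses a different window. Under SAP 4.1.7 and 4.1.11, exacerbations and the offset run to the End of Treatment Visit. For those who leave early, "Date of treatment discontinuation will be the date of End of Study Visit", or of the last Study Visit if the subject is lost to follow-up.

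Protocol 8.7 states that "IMP administration may be temporarily interrupted during the time of systemic antibiotic treatment due to a pulmonary exacerbation", on the investigator's judgement. SAP 4.5.5 derives the days of interruption, but only to summarise them.

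The 80% threshold decides who enters two rate analyses. The Per-Protocol Population (SAP 3.5.4) takes mITT subjects who "had an adherence of at least 80" per cent and had no major deviation affecting efficacy. The rerun of the primary analysis in SAP 4.7.4.3 uses the same threshold with no deviation screen. For the adherent analysis in SAP 4.7.6.1 the rule differs: those subjects "had an adherence until the first pulmonary exacerbation of at least 80" per cent.

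**The concern.** Two features of one definition pull in opposite directions.

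- **Early stoppers can pass.** Days after the last dose are not scheduled doses, yet exacerbations and time on those days still count in the rate. Adherence and outcome then cover different windows. The score can also turn on one dose, because a supervised Visit 7 dose extends the denominator to the full year and its absence does not.
- **Exacerbators can fail.** When IMP is interrupted for an exacerbation, each undosed day counts as two missed doses. Membership of the set then depends partly on the outcome analysed in it, and unequally by arm if the drug works. SAP 4.7.6.1 avoids this by stopping the clock at the first exacerbation; the rate analyses do not.

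Readers will look at these analyses. In the predecessor trial the adherent subset gave p=0.028 against 0.11 overall (Protocol 3, Trial Rationale), and SAP Addendum section 3 cites the internal consistency required of an application resting on a single pivotal study.

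**Working it through.** **Inputs.** The adherence formula is from SAP 4.5.4. Arm rates of 1.2701 and 0.8256 per year and over-dispersion 0.273 are from SAP 3.9. The documents give no interruption frequency, interruption length or adherence distribution for this trial, so those are assumptions shown as ranges. Protocol 9.1.5 mentions an initial 14-day antibiotic course, which supports 14 days as a course length but does not show that IMP is stopped for all of it.

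**Check of the reused inputs.** The negative binomial Wald formula is n = (z₀.₉₇₅ + z₀.₉₀)² × [(1/1.2701 + 1/0.8256) + 2 × 0.273] / [ln(0.8256/1.2701)]². It gives 144.1, or 145 per arm after rounding up, which is the SAP 3.9 figure.

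**Early stopper: 115 of 120 doses over the first 60 days, then none.**
- No later dose, SAP rule: 115/120 = 95.8%, whenever follow-up ends.
- Same subject measured to an End of Study Visit at day 180: 115/(2 × 181) = 31.8%.
- Same subject with one supervised dose at a day-365 Visit 7, SAP rule: 116/(2 × 366) = 15.8%.

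**Interruptions.** With underlying adherence a and e fully interrupted 14-day courses in 365 days, the score is a × (365 − 14e)/365. For e = 0, 1, 2, 3:
- a = 85%: 85.0, 81.7, 78.5, 75.2%.
- a = 90%: 90.0, 86.5, 83.1, 79.6%.

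The interrupted days that a subject can have before falling below 80% are 365 × (1 − 0.8/a): 73 at a = 100%, 57.6 at 95%, 40.6 at 90% and 21.5 at 85%. In fully interrupted 14-day courses, it takes 6, 5, 3 and 2 respectively to fall below.

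**How common such event counts are.** A negative binomial with the SAP's rates and dispersion over one year gives P(2 or more) = 34.7% on placebo and 20.5% on active, and P(3 or more) = 15.7% and 6.8%. These are probabilities of events, not of exclusion.

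**Effect on the rate ratio in the set.** Simulation over a full year; underlying adherence assumed Beta(12,2), under which 77% of subjects reach 80%; each course wholly interrupted with a given probability; true ratio 0.65:
- 14-day courses, 25%, 50% or 100% interrupted: ratio about 0.65, 0.67 and 0.70–0.71. The share of subjects with three or more events who stay in the set falls from about 76% to about 66%, 54–56% and 25–29%.
- 21-day courses, all interrupted: about 0.75.
- No interruptions: no change.

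With higher assumed adherence (Beta(38,2), 99.8% at or above 80%), the ratios when all courses are interrupted are about 0.70 (14 days) and 0.74 (21 days). Every shift is toward the null.

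**The case against.** Several limits stand.

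- **The Visit 7 dose.** Protocol 8.5 has a supervised dose at Visit 7. A completer who takes it has a full-year denominator, and a stopper among them scores about 16%. A reader might infer that anyone who abandons IMP counts as adherent. The documents support that only for subjects with no later counted dose: withdrawals, a missed Visit 7 dose, or a split Visit 7 whose late dose is dropped.
- **Long gaps should be noticed.** Device data are reviewed at Visits 3 to 6, low adherence prompts retraining (Protocol 9.2), and poor adherence is a possible reason for withdrawal (Protocol 14). The planned drop-out of about 20% is an upper limit for withdrawals, since someone who doses until withdrawal has almost no gap.
- **The Per-Protocol deviation screen.** SAP 3.5.4 names IMP not given as the protocol defines, and SAP 4.10.1 lists dosing and compliance categories. A reader might infer that Per-Protocol admits every stopper, but this screen may remove some. Its exact definitions are left to blind review, so how many is unknown. The adherent subgroup has no such screen.
- **Interruption is optional.** Protocol 8.7 also allows antibiotics on top of continued IMP. A reader might infer that following the protocol costs adherence at every exacerbation; it does so only when IMP is actually interrupted.
- **Related summaries exist.** Extent of exposure, interruption days and time to discontinuation are tabulated by arm, and reporting on-drug adherence apart from persistence is a legitimate choice for a descriptive table. It is weaker as a rule for who enters an outcome analysis that runs past the last dose.

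These points limit how often the problem arises and how large it is. They do not change what the formula does.

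**Conclusion.** The point holds as a defect in the definition behind supportive analyses. SAP 4.5.4 can class a subject who stopped IMP as at least 80% adherent (95.8% against 31.8% in the example). It can also remove a subject at about 85–90% underlying adherence after two or three interrupted exacerbations. SAP 4.7.4.3 is exposed most directly; SAP 3.5.4 is exposed subject to its deviation screen.

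The interruption effect is modest on assumed inputs: from 0.65 to about 0.65–0.70 with 14-day courses, and about 0.75 only if every course lasts 21 days and is wholly interrupted. It attenuates the apparent benefit and does not flatter it. The direction and size of the early-stopper effect cannot be derived from the documents. A reader might infer that the trial's main conclusion is in doubt; it is not touched by this, because the primary analysis is on mITT and uses no adherence cut.

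**What to change.** Derive a second adherence variable as follows.

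- Set the end of period to the treatment completion or discontinuation date of SAP 4.1.7, using the remote call date for a split Visit 7.
- Count only doses up to that date. Otherwise a subject lost to follow-up, whose window closes at the last Study Visit, could keep later logged doses in the numerator.
- Subtract from scheduled doses two per undosed day within a documented IMP interruption for an exacerbation. Do not reuse the SAP 4.5.5 count: it is re-start minus stop plus 1, and in its device-log form both end dates are dosing days.

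Rerun the adherent-subgroup and Per-Protocol rate analyses on this variable beside the planned ones, and show both adherence distributions. SAP Addendum 2.2 records that the study is unblinded, so under SAP section 1 the rerun must be labelled post hoc.

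The cost is one extra derived variable from data already held and the repeated outputs. The adherent share may look lower.

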4.5.5 IMP interruptions

The number and percentage of subjects with at least one IMP interruption, the number and percentage of subjects with at least one IMP interruption due to NCFB pulmonary exacerbation and the number of NCFB pulmonary exacerbations which lead to an IMP interruption will be presented.

Moreover, the number of days of IMP interruption overall and due to NCFB pulmonary exacerbations will be summarised using descriptive statistics for continuous variables.

Results will be presented overall and by treatment group for the Safety and mITT Populations.

Notes:

- NCFB pulmonary exacerbations will be linked to the corresponding AE using the AE number collected in the eCRF form "Pulmonary Exacerbation", i.e. "Please specify corresponding Adverse Event number for this Pulmonary Exacerbation".
- IMP interruption (days) will be calculated considering stop date and re-start date of IMP as collected in the eCRF "Adverse Event" form using the following formula:

$$\text{IMP interruption (days)} = \text{Re-Start date of IMP} - \text{date of Stop of IMP} + 1.$$
- If any dose with a dose different than "Null" is recorded in the **CCl** logging system during this period, then the **CCl** data will be considered to compute IMP interruption: stop date will be the last IMP dose date before the start of the AE, re-start date will be the first IMP dose date after the start date of the AE.

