11.2. INVESTIGATIONAL MEDICINAL PRODUCT DISPENSING AND ADMINISTRATION

Subjects will administer the first dose of the IMP at the investigational site under the supervision of the site staff, and will be instructed by the Investigator or a delegated person how to prepare and self-administer the IMP at home via the CCI system, twice daily (morning and evening) over a period of 12 months. At least 10 minutes prior to each administration, an inhaled short-acting bronchodilator (e.g. salbutamol/albuterol) should be taken to improve tolerability. When the first dose is administered at the investigational site, subjects will have their FEV₁ monitored pre-bronchodilator and 30 ± 10 minutes post-IMP dose to investigate if there is any evidence of bronchospasm (defined as a decrease >15% in FEV₁ – not due to poor technique - from pre-bronchodilator baseline).

Subjects experiencing a decrease in FEV₁ >15% from pre-bronchodilator baseline and/or clinically determined bronchospasm after receiving their first dose of IMP, will be withdrawn from the trial.

The subject will administer the IMP at home twice daily (morning and evening) about at least 10 minutes after inhaled short-acting bronchodilator administration. If the patient does not wish to use the bronchodilator and tolerates the IMP without it, this is acceptable but should be documented appropriately.

The IMP must be reconstituted by carefully removing the red plastic cap on top of the vial and the attached aluminium collar seal, and injecting the 1 mL saline through the rubber stopper into the vial using a syringe provided by the CRO to each site. The vials must not be shaken but gently rolled between both hands to facilitate the dissolving of the powder. After 5 minutes of rest, the stopper can be opened and all of the solution transferred into the CCI chamber (with a 0.3 mL dosing chamber). Active treatment and placebo solutions are identical so that neither the Investigator nor the subject can recognize the identity of the product.

The instructions for preparation and administration of the IMP through the CCI device will be described in detail in an information leaflet for participating subjects.

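### The SAP's IMP interruption formula counts dosing days as interruption and, when device data are used, ties the dates to AE onset instead of the actual gap, so the reported days are wrong in either direction

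*SAP*

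**What the plan says.** SAP section 4.5.5 reports the number of days of IMP interruption, overall and due to exacerbations, for the Safety and mITT populations. The default rule is that "IMP interruption (days) will be calculated considering stop date and re-start date of IMP as collected in the eCRF" Adverse Event form, and the formula is re-start date minus stop date plus 1. The section does not say whether the stop date is the last day dosed or the first day off.

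A second rule replaces the eCRF dates when the device log contradicts them. Its trigger begins "If any dose with a dose different than 'Null' is recorded in the" logging system during the recorded period. Under it, "stop date will be the last IMP dose date before the start of the AE" and "re-start date will be the first IMP dose date after the start date of the AE". No separate formula is given for this branch, so the same plus 1 applies.

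Two other statements bear on the result. Protocol section 8.7 says that "IMP administration may be temporarily interrupted during the time of systemic antibiotic treatment" for an exacerbation, at the investigator's judgement. SAP section 2.1 dates the exacerbation from the first day of qualifying symptoms, not from the start of antibiotics or the day IMP was stopped.

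**The concern.** Adding 1 is right when both end dates belong to the interval. The SAP uses it that way for extent of exposure (4.5.3) and for antibiotic course duration (4.7.4). An interruption is the space between doses, so days on which the subject dosed do not belong to it. In the device branch both end dates are dosing days by definition, and the formula counts both.

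The second problem is the anchor. The device rule looks for the doses on either side of AE onset, not for the gap. If the subject keeps dosing for a few days after symptoms begin and then stops, the rule measures a short stretch around onset and misses the interruption.

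What is at stake is the accuracy of two exposure tables that a reader would use to judge how long treatment was suspended, in particular around exacerbations.

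**Working it through.** The plan gives no numerical interruption figure to reproduce, so the rule was applied to constructed dosing calendars.

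**Inputs.** Formula and both date rules: SAP 4.5.5. Dosing twice daily: protocol 11.2. Assumed for illustration: AE onset on day 10, and two doses on every day not listed as off.

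**Device branch**, result = re-start − stop + 1:

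| Days fully off | Stop | Re-start | SAP result | Fully dose-free days | Error |
|---|---|---|---|---|---|
| None | 9 | 11 | 11 − 9 + 1 = 3 | 0 | +3 |
| 10 | 9 | 11 | 11 − 9 + 1 = 3 | 1 | +2 |
| 10–16 | 9 | 17 | 17 − 9 + 1 = 9 | 7 | +2 |
| 10–23 | 9 | 24 | 24 − 9 + 1 = 16 | 14 | +2 |
| 11–17 | 9 | 18 | 18 − 9 + 1 = 10 | 7 | +3 |
| 13–20 | 9 | 11 | 11 − 9 + 1 = 3 | 8 | −5 |
| 12–25 | 9 | 11 | 11 − 9 + 1 = 3 | 14 | −11 |

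A dose on the onset day itself is neither before nor after that date, so both of the rule's dates skip it. If it were taken as the re-start, the result would be 10 − 9 + 1 = 2 in every row with dosing on day 10. That does not repair the later gaps.

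Once dosing continues through the day after onset, stop and re-start are fixed at days 9 and 11. Later gaps of 1, 3, 7 and 14 days all return 3.

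**eCRF branch**, off days 10–16 (7 days), re-start day 17:

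- stop = first day off: 17 − 10 + 1 = 8, an excess of 1;
- stop = last dosing day: 17 − 9 + 1 = 9, an excess of 2.

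**Partly dosed boundary days.** Last dose on the morning of day 9, re-start on the evening of day 17: 17 − 9 + 1 = 9. Against this there are 7 fully dose-free days, 16 missed doses (16 / 2 = 8 dose-days) and 9 days with any dose missed. The excess is therefore 2, 1 or 0, depending on a definition that the SAP does not give.

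**Would changing the constant be enough?** No. With minus 1 in place of plus 1, the device dates give 11 − 9 − 1 = 1 when nothing was missed, and also 1 for the gap on days 12–25. Counting dose-free days between the same two dates gives 0 for that 14-day gap.

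**The case against.** Several readings go further than the documents allow.

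- **That the rule overstates every interruption.** It does not. Protocol 8.7 ties interruption to the antibiotic course, and SAP 2.1 dates the event from symptoms, so stopping some days after onset is plausible. Those gaps can be understated.
- **That the formula creates interruptions for subjects in general.** The device dates are used only where the eCRF already records a stop and re-start. The failure is narrower: a recorded interruption that the log refutes is not set to zero.
- **That the excess is always two days.** That holds for the device branch when the gap starts on the onset day and only fully dose-free days count. The eCRF excess is 1 or 2 days, depending on form instructions that are not in the documents. With partly dosed boundary days the device figure can even match the days with any missed dose.
- **That the arm with more exacerbations is inflated more.** The documents give no interruption data by arm, interruption is left to the investigator, and the error can go either way. This should not be claimed.

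It can also be said that lost treatment is measured better elsewhere. Adherence (SAP 4.5.4) uses dose counts, exposure days (4.5.2) count days with a dose, the per-protocol 80% criterion uses adherence, and the primary model's offset uses follow-up time. None uses this variable. That is correct and limits the consequence, but it does not make the reported interruption days right.

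**Conclusion.** The derivation is wrong as written. In the device branch it reports 3 days when no dose was missed, adds 2 to the fully dose-free days of a gap starting on the onset day, and returns 3 for any gap starting two or more days later (3 against 14 in the example). In the eCRF branch it adds 1 or 2 days, depending on what the stop date means.

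These sizes assume that an interruption day is a calendar day with no dose. The device figures also assume that the branch is reached, meaning that a non-Null dose falls within the recorded period. The SAP does not say whether a dose on a boundary date of that period counts, and the documents do not show how often the branch would apply. The total error in the tables therefore cannot be estimated.

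The consequence is confined to descriptive Tables 14.1.13.1 and 14.1.13.2. The primary analysis, adherence and the per-protocol set are untouched.

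**What to change.** Rewrite the note in SAP 4.5.5 as follows.

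- **Device data available:** count the calendar days with no recorded non-Null dose within the actual gap or gaps in the log over the eCRF-recorded interruption period, extended to the adjoining dose-free days. Report 0 if there are none. Do not take the dates from the doses on either side of AE onset.
- **eCRF dates only:** define stop as the first day not dosed and use re-start minus stop.
- **Both:** state that partly dosed days are not counted.

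In the examples this gives 0 for no missed dose, 7 for days 10–16 and 14 for days 12–25 from the log. From eCRF dates it gives 17 − 10 = 7 for days 10–16.

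The cost is one revised derivation and a re-run of two descriptive tables. The SAP Addendum records that the study has been unblinded, so the change would be documented in the clinical trial report as a post hoc deviation, as SAP section 1 requires. If the tables are not re-run, a footnote should state the rule used and its known errors.
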